We plan to recruit 24 English-speaking participants aged 50 years and older with aMCI and a history of TBI, all of whom have problems with episodic memory. Participants can be referred from identified providers at UT Southwestern Medical Center, Parkland Health & Hospital System, Veteran's Affairs Hospitals, or other locations in the DFW area with providers that are aware of this research effort. All recruitment procedures will take place at UTSW locations, as well as all research visits. All participants will have at least 12 years of education and a history of TBI as determined by VA/DOD criteria. Participants will be randomized into an active HD-tDCS condition or a sham condition with a 2:1 ratio of active (n=16) to sham (n=8) participants in order to assess the efficacy of HD-tDCS on improving episodic memory. The proposed study will measure response to treatment with 1 mA anodal HD-tDCS over the preSMA/dACC region when compared to sham. Participants will receive 10 sessions of active stimulation (1 mA anodal HD-tDCS targeting preSMA/dACC for 20 min) or sham across 2 weeks. Episodic memory tasks will be completed at baseline, immediate follow-up after session 10, and a 3-month follow-up.

Visits

Below is a table summarizing the study visits followed by a detailed description of the procedures for each visit. It is a 12 day study with a follow-up session twelve weeks after the last day.

TABLE 1. SUMMARY OF VISITS

| Visit | PROCEDURES | TIME |
|-------------|---|-------------------|
| Visit 1 | Pre-testing neuropsychological assessment | 1 hour |
| Visits 2-10 | HD-tDCS active or sham stimulation | 30 minutes |
| Visit 11 | HD-tDCS active or sham stimulation and post-testing neuropsychological assessment | 1 hour 30 minutes |
| Visit 12 | 12-week follow-up assessments | 1 hour |

Visit 1: Pre-testing neuropsychological assessment (approximately 1 hour)

Assessments: At UTSW's Cognitive and Memory Disorders Clinic, participants will first be asked to complete the Ohio State University TBI Interview Method (OSTBIIM) to characterize TBI history and severity. Afterwards, a neuropsychological evaluation will be completed consisting of the following measures:

1. Hopkins Verbal Learning Test-Revised (HVLT-R)
2. Brief Visuospatial Memory Test-Revised (BVMT-R)
3. Controlled Oral Word Association Test
4. Wechsler Adult Intelligence Scale-IV Digit Span
5. Trail Making Test
6. Stroop Color and Word Test
7. Beck Depression Inventory-2

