This study may contribute to developing a new non-pharmacological method for the treatment of episodic memory difficulties in individuals with aMCI following traumatic brain injury. Given only a slight risk to participants and the greater possibility of long-term benefits to the knowledge base, the risks/benefits ratio seems reasonable.

14. Biostatistics:

Linear mixed modeling (LMM) will be used to assess performance growth as a function of group (i.e., number of sessions) and assessment period. Primary outcomes will be measures of episodic memory from the neuropsychological battery. Additionally, baseline assessments on neuropsychological measures, TBI severity, use of cholinesterase inhibitors, and demographics variables will allow for assessing individual differences prior to the intervention as a predictor of response to the proposed treatment schedules. LMM will allow for testing change scores from baseline as a function of group and assessment session. Obtaining combined linear and quadratic fit parameters will allow for estimating points of asymptote in the gain functions per outcome to identify optimal delivery protocol parameters. We will use restricted maximum likelihood estimators (ReML) of the variance components to compute the maximum likelihood estimators of the fixed effects parameters (i.e., group, session, and group*session interaction effects). Thus, we will not exclude participants with missing time points. All available data on all participants who 1) meet inclusion/exclusion criteria, 2) have been randomly assigned to groups, and 3) provide baseline data will be used regardless of whether they complete the trial. (Depending on the amount of dropout, analyses also will be carried out to identify any biases in dropouts per group.)

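### Section 14 equates the randomised group with number of sessions, which is 10 in both arms, and promises a delivery optimum that the design cannot identify

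*Combined protocol and SAP*

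**What the plan says.** Section 14 (Biostatistics) is the only statistical section. It sets out a linear mixed model to "assess performance growth as a function of group (i.e., number of sessions) and assessment period". It then speaks of baseline characteristics "as a predictor of response to the proposed treatment schedules", in the plural, and says that combined "linear and quadratic fit parameters will allow for estimating points of asymptote in the gain functions per outcome to identify optimal delivery protocol parameters". The same section also describes "testing change scores from baseline as a function of group and assessment session" and lists the fixed effects as "group, session, and group*session interaction effects".

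The design is in Section 4 (Study Procedures), Overview and design:

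- Allocation: "Participants will be randomized into an active HD-tDCS condition or a sham condition with a 2:1 ratio of active (n=16) to sham (n=8) participants".
- Schedule: "Participants will receive 10 sessions of active stimulation (1 mA anodal HD-tDCS targeting preSMA/dACC for 20 min) or sham across 2 weeks".
- Outcome timing: "Episodic memory tasks will be completed at baseline, immediate follow-up after session 10, and a 3-month follow-up".

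The visit descriptions in Section 4 agree: Visits 2 to 10 and Visit 11 each carry one active or sham session. There is one active current, one target and one session length.

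**The concern.** There are two separate faults.

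First, the parenthetical defines group as something the trial does not randomise. Scheduled sessions are the same in both arms. Sessions actually attended would differ only through non-adherence, which is not randomised. Neither can carry the active-vs-sham comparison that is the study objective.

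Second, the linear-plus-quadratic sentence promises a result about delivery when no delivery parameter is varied and memory is never tested between sessions 1 and 10. A turning point reported from such a fit would be driven largely by when the visits fall and how time is coded, and would say nothing about stimulation dose. This is a pilot, so a spurious optimum could be carried into the design of a later trial.

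**Working it through.** **The plan's own figures.** Visits 2 to 10 give 9 sessions and Visit 11 gives 1, so 9 + 1 = 10 in each arm. Allocation 2:1 of 24 gives 24 × 2/3 = 16 and 24 × 1/3 = 8. Both agree with the protocol. No effect size, SD or power is stated, so there is no power figure to reproduce.

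**Step 1: what group can estimate.** Take the columns intercept, two assessment indicators, group, and group times each indicator: six columns.

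| Coding of group | Rank |
|---|---|
| Scheduled sessions (10 in both arms) | 3 of 6 |
| Active vs sham | 6 of 6 |

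With group equal to 10 for everyone, the last three columns are multiples of the first three, so no group effect exists to estimate.

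**Step 2: a curve in sessions.** Cumulative sessions s at the three assessments are 0, 10 and 10. The columns 1, s, s² take only two distinct rows, so the rank is 2 of 3 (4 of 6 when crossed with arm). For illustration, assume exponential gain curves that reach 95% of the post-treatment gain after 2, 6 or 9 sessions. All three pass through the same values at 0 and 10 sessions, so these data cannot tell them apart.

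**Step 3: a curve in time.** Linear plus quadratic in time crossed with arm has rank 6 for six cell means and spans the same space as the three-level factor crossed with arm. It is a valid model of the means, but no degree of freedom remains to check the shape.

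**Step 4: where the turning point falls.** Assume assessments at weeks 0, 2 and 14, a gain g at week 2, and a fraction r of it remaining at week 14. The quadratic at² + bt through (0, 0), (2, g), (14, rg) has

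- a = −g(7 − r)/168 and b = g(49 − r)/84;
- turning point −b/(2a) = (49 − r)/(7 − r);
- height there = g(49 − r)²/[168(7 − r)].

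| Gain kept at week 14 | Turning point | Height | Height if g = 3 |
|---|---|---|---|
| All (r = 1) | 48/6 = week 8.0 | 2304/1008 = 2.29g | 6.9 |
| Half (r = 0.5) | 48.5/6.5 = week 7.5 | 2352.25/1092 = 2.15g | 6.5 |
| None (r = 0) | 49/7 = week 7.0 | 2401/1176 = 2.04g | 6.1 |

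Full retention and full loss move the peak by one week. In each case it lies well after stimulation has ended, where nothing is measured. For g > 0 the peak lies between weeks 2 and 14 whenever −35 < r < 49/13 = 3.77.

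**Step 5: sensitivity to timing and coding.** Section 4 also calls this a 12-day study with follow-up twelve weeks after the last day. Taking days 0, 11 and 95 (11 + 84), the peak is at (11 + 95)/2 = day 53 (week 7.6) with height 2.69g for r = 1, and at 95/2 = day 47.5 (week 6.8) with height 2.44g for r = 0.

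With visits coded 0, 1, 2, the turning point is (4 − r)/[2(2 − r)] and the height g(4 − r)²/[8(2 − r)]. For r = 1 this is visit 1.5 at 1.125g (3.4 if g = 3, against 6.9 above). For r = 0 it is visit 1.0, which is week 2, at 1.0g (against week 7.0 at 2.04g). The same means give different peaks under different codings.

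**The case against.** The strongest reply is that the parenthetical can be rescued. If it means scheduled active sessions, the arms have 10 and 0. That is the active/sham indicator multiplied by 10, and the design has full rank. The context helps this reading: Section 4 states the randomised factor plainly, Section 14 refers to random assignment to groups, and it uses assessment period and assessment session in ways that suggest what session means in the fixed-effects list. On this view the first fault is a slip of wording.

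Part of this stands. The efficacy model is recoverable, and the rank of 3 of 6 applies to the literal reading only. But the rescue needs the word active inserted, while Section 4 itself calls the sham visits sessions. Even then the variable is a rescaled arm indicator: added to that indicator it gives three columns of rank 2, so it carries no dose information.

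A second reply is that the turning-point figures are illustrative: the plan fixes neither the time axis nor a rule that the turning point will be reported as the asymptote, and under visit coding the peak can fall on a real assessment. That is correct, and the size of the distortion depends on the coding chosen. The non-identifiability does not: it follows from 0, 10 and 10 sessions at testing and from no delivery parameter being varied.

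A third reply is that deleting the sentence loses a legitimate trend description. It loses nothing estimable, because over three assessments the polynomial and the three-level factor are the same model of the means.

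**Conclusion.** The concern holds and should be fixed. Taken literally, group as number of sessions is constant at 10 and cannot carry the active-vs-sham comparison. The asymptote and optimal-delivery result is not identifiable under any reading of group.

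The rank results need only the design as stated. The turning-point figures rest on an assumed gain, assumed retention and assumed visit timing. The multiples of g do not depend on the size of the gain.

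The scope is narrow: the parenthetical, the plural reference to schedules, and the asymptote sentence. The group-by-assessment efficacy comparison is fully estimable once group is read as randomised arm and session as assessment. The trial's main comparison is not in doubt.

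**What to change.** In Section 14:

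1. Replace the gloss on group with: active vs sham, as randomised.
2. State that session in this section means assessment, and model it as a three-level categorical factor (baseline, immediate follow-up, 12 weeks). Read efficacy from the active-minus-sham contrasts in change from baseline.
3. Delete the sentence on asymptotes and optimal delivery parameters.
4. Replace the reference to proposed treatment schedules with active vs sham treatment.

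The cost is the wording of one section, with no new data, visits or participants. The trial gives up a dose-optimisation claim that its design cannot support.

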For the active condition, administration parameters will consist of the stimulation being ramped up over 60 seconds until it reaches 1 mA, maintained for 20 minutes, and then ramped down over 60 seconds at each session. The anode will be placed over Fz according to the International 10-20 EEG system, corresponding to the approximate location of the preSMA/dACC. Four return cathodal electrodes will be placed approximately 5 cm radially from Cz; corresponding to locations Fz, FPz, F7, F8 and Cz. 20 minutes of 1 milliamp of anodal HD-tDCS per session.

For the sham condition, parameters will consist of current being ramped up over 60 seconds until it reaches 1 mA and then stopped. (This allows for the same scalp sensation for both the sham and active condition so that subject and experimenter will remain blinded). This ramp up for one minute and then stopped and off for 19 minutes will be given each 20-minute sham session to keep the timing and subjective experience similar to the active condition.

Visit 11: HD-tDCS active or sham stimulation + Post-assessment (1 hour and 30 minutes)

HD-tDCS Stimulation: Participants will receive a final session of either active stimulation (1 mA anodal HD-tDCS targeting preSMA/dACC for 20 min) or sham. The stimulation current will gradually ramp up to 1mA during the first 60 seconds of stimulation, and remain for 19 minutes in the active stimulation group, but turned off afterwards for the sham group. Participants will also undergo the same neuropsychological assessments as in Visit 1.

Visit 12: 12-week Follow-up Neuropsychological Assessments

After 3 months from their last session, post-neuropsychological assessment will be completed to see if previously acquired gains remain over this time frame. Neuropsychological measures will be the same as in Visit 1.

Summary of Study Team's Experience Using HD-tDCS:

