A source of research material is the data registry of UTSW's Cognitive and Memory Disorders Clinic. The Clinic collects sociodemographic, apolipoprotein E, medical, and clinical information from individuals diagnosed with aMCI. We will obtain data about clinical diagnosis, date of birth, prior medical conditions, and apolipoprotein E status from the data registry. Because only a limited information about TBI has been collected in this data registry (e.g., presence/absence of TBI with LOC > or < 1 year ago), we will administer the Ohio State University TBI Interview Method (OSTBIIM) at a Study Visit to characterize each participant's TBI history and severity.

The following assessments will be completed at a Study Visit at UTSW's Cognitive and Memory Disorders Clinic for the purpose of the study:

- Episodic verbal memory will be assessed with the Hopkins Verbal Learning Test-Revised (HVLT-R). This measures rate of learning for verbal material and the amount retained after a delay.
- Episodic visual memory will be assessed with the Brief Visuospatial Memory Test-Revised (BVMT-R). This measures rate of learning for visual material and the amount retained after a delay.
- Controlled Oral Word Association Test to measure word retrieval within specific search parameters
- Wechsler Adult Intelligence Scale-IV Digit Span to measure attentional capacity and working memory.
- Trail Making Test to measure information processing speed as well as mental flexibility as part of executive functioning.
- Stroop Color and Word Test to measure information processing speed as well as selective attention and response inhibition as part of executive functioning.
- Beck Depression Inventory-2 to evaluate the extent of depressive symptomatology present.

9. Recruitment Methods and Consenting Process:

Providers around the DFW area who work closely with UTSW's researchers are a valuable source of referrals. Utilizing clinics outside of UTSW maximizes the participant pool while also providing a service to a greater population. Referral of participants may originate from identified providers at UT Southwestern Medical Center, Parkland, Veteran's Affairs Hospitals, or other locations in the DFW area with providers that are aware of this research effort. All recruitment procedures will take place at UTSW locations, though referrals may originate from clinics outside of UTSW. All research visits will take place at UTSW.

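### Does Section 14 need a single named primary test because it makes several episodic memory measures primary with no alpha or multiplicity rule?

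*Combined protocol and SAP*

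**What the plan says.** Section 14 (Biostatistics) is the whole statistical plan. On outcomes it says "Primary outcomes will be measures of episodic memory from the neuropsychological battery", in the plural. On the analysis it says "LMM will allow for testing change scores from baseline as a function of group and assessment session", and it lists the fixed effects as "group, session, and group*session interaction effects". It adds curve fitting: "Obtaining combined linear and quadratic fit parameters will allow for estimating points of asymptote in the gain functions per outcome". It gives no alpha, sidedness, composite, testing order or adjustment, and neither does any other section.

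Other sections narrow the reading:

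- Section 8 (Sources of Research Material) labels two tests in the battery as episodic memory: the HVLT-R (verbal) and the BVMT-R (visual). Of the HVLT-R it says "This measures rate of learning for verbal material and the amount retained after a delay", and it describes the BVMT-R in parallel terms for visual material.
- Section 4 (Study Procedures) sets the schedule: "Episodic memory tasks will be completed at baseline, immediate follow-up after session 10, and a 3-month follow-up". It randomizes 16 to active and 8 to sham "in order to assess the efficacy of HD-tDCS on improving episodic memory".
- Section 4, under Visit 12, gives the later visit a maintenance role: "post-neuropsychological assessment will be completed to see if previously acquired gains remain over this time frame".
- Section 3 (Concise Summary) states the objective as the effect after 10 sessions.
- Section 1 calls the study a pilot, and Section 2 describes its aim as exploratory.

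**The concern.** A plural primary outcome with no deciding test lets the analyst choose after seeing the data. The candidates include two instruments, possibly a learning and a retention score from each, two follow-up times, and several model terms. If any nominally significant result among them could be reported as the primary finding, the false-positive rate is not the level of a single test, and no pre-specified rule would let a reader check the choice. The pilot label does not fully answer this, because Sections 1, 3 and 4 speak of efficacy. With only 8 participants on sham, a chance result on one score could be presented as the main result.

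**Working it through.** The plan states no alpha, power or effect size, so there is no figure of its own to reproduce. The check has two parts: how many primary tests the text supports, and what that number implies.

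**How many tests**

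1. Instruments: Section 8 labels two as episodic memory.
2. Effect: the between-arm question in a model with group, session and their interaction is the interaction, that is, whether change from baseline differs by arm. Group alone mixes in the baseline difference, and session alone is not a comparison of arms.
3. Time: Section 3 puts the objective after 10 sessions, and the Visit 12 text gives the 12-week assessment a maintenance role. The immediate follow-up therefore leads by implication, though no order is stated.
4. Scores: Section 8 describes what each instrument measures (learning and retention). It does not list scores to be analysed. Two scores per instrument, hence 2 × 2 = 4, is a possible reading but is inferred from that description.

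The best-supported count is two tests, and four is the wider reading. Crossing four scores with two follow-ups gives 4 × 2 = 8 contrasts, but this ignores points 2 and 3.

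**What it implies**

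Inputs: 16 and 8 participants (Section 4). Assumed: two-sided 0.05 per test, no adjustment, complete data, no true effect, and a range of correlations between outcomes.

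With independent outcomes the chance of at least one false positive is 1 − (1 − 0.05)^k:

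- k = 2: 1 − 0.95² = 0.0975
- k = 4: 1 − 0.95⁴ = 0.1855

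With correlated outcomes, from simulated pooled t tests on 16 v 8 (22 df):

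| Tests | Correlation assumed | Any false positive |
|---|---|---|
| 2 | 0 | 9.7% |
| 2 | 0.5 | 9.2% |
| 2 | 0.9 | 7.1% |
| 4 | 0.5 within an instrument, 0.3 between | 16.9% |
| 4 | 0.7 within, 0.5 between | 14.8% |
| 4 | 0.9 within, 0.7 between | 11.6% |

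Two tests give about 7% to 10%, and four correlated scores about 11.5% to 17%. The independence figure of 18.5% for four requires learning and retention on the same instrument to be uncorrelated, which is not realistic. Testing the 2-df interaction instead of a t test on change gives nearly the same result for two outcomes: 7.3% at correlation 0.9 and 9.8% at 0.

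**What adjustment would cost**

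For a two-sample t test with 16 and 8, the standard error of the difference is SD × √(1/16 + 1/8) = 0.433 SD. The difference detectable with 80% power (noncentral t, 22 df) is 1.27 SD at 0.05 and 1.42 SD at 0.025, the first Holm step for two tests. The increase is 1.42 − 1.27 = 0.15 SD, on a threshold that is already very large.

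**The case for a change.** The strongest case for a change is that the study states an efficacy purpose and designates primary outcomes, so it should say what the primary comparison is. The reasoning above narrows the effect and the time point, but nothing in the text chooses between verbal and visual memory, or between learning and retention. One or two sentences in Section 14 before unblinding would settle this without touching visits, tests or sample size, and would prevent selection after the fact.

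Much of this stands. The deciding score, the alpha and the testing order are not written down, and no redaction or gap in Section 14 explains their absence. Recording a choice before unblinding would be good practice. The false-positive figures are also correct under their assumptions.

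What does not stand is the step from a thin specification to a defect. The inflation arises only if each result is tested at an unadjusted 0.05 and any one success counts, and the plan commits to neither. The documents do not determine which score should lead, so a reviewer could only ask the sponsor to pick one. The concrete statistical alternative, adjustment across two instruments, gives up sensitivity in a trial that has little.

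**Conclusion.** The plan is under-specified here, but no change follows. It names the model, the interaction and change from baseline. It labels two instruments as episodic memory, and it implies that the assessment after session 10 leads. A competent analyst would fit the same model to the HVLT-R and the BVMT-R, report both active-versus-sham differences in change with confidence intervals, and treat the 12-week results as supporting information.

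The size at issue is a 7% to 10% chance of any false positive on the best-supported count of two tests, and about 11.5% to 17% if each instrument contributes two scores, against 5% for one test. These rates rest on an assumed two-sided 0.05, no adjustment, complete data and the correlations shown. The documents supply none of these.

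The plan states no error rate, power or decision rule that the design contradicts. With 16 v 8 and a detectable difference of about 1.27 SD even for a single test, the result would be read as pilot evidence whichever score led. Strict family-wise control is a matter of judgement in that setting. A reader of the eventual report should expect both instruments to be shown and should discount a claim built on one score alone.

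### The planned analysis of predictors of response has no group-by-predictor term, so change that active and sham participants share can be read as response to stimulation

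*Combined protocol and SAP*

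**What the plan says.** Section 14 (Biostatistics) lists "baseline assessments on neuropsychological measures, TBI severity, use of cholinesterase inhibitors, and demographics variables" and says that these "will allow for assessing individual differences prior to the intervention as a predictor of response to the proposed treatment schedules". The next sentence sets the scale of analysis: "LMM will allow for testing change scores from baseline as a function of group and assessment session". The fixed effects are then given as "i.e., group, session, and group*session interaction effects". No separate predictor model is described.

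The outcomes come from the same battery as the baseline predictors: "Primary outcomes will be measures of episodic memory from the neuropsychological battery". That battery is repeated. Under Visit 11 in Section 4, "Participants will also undergo the same neuropsychological assessments as in Visit 1", and Visit 12 uses it a third time. No alternate forms are mentioned.

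Section 4 (Overview and design) gives the size, "We plan to recruit 24 English-speaking participants aged 50 years and older with aMCI and a history of TBI", and the allocation, a "2:1 ratio of active (n=16) to sham (n=8) participants". The same paragraph says that response to active stimulation will be measured against sham.

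**The concern.** A predictor of response to stimulation is a trait for which the active-minus-sham difference varies. Estimating it needs a group-by-predictor term. Without one, a predictor can be related only to level or to change over time. Change also contains practice, regression to the mean and natural course, which sham participants have too.

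Baseline memory has a further problem, because the predictor is the quantity subtracted to form the outcome. A low baseline score goes with a larger gain even when stimulation does nothing. In this trial everyone is enrolled with an episodic memory problem and takes the same tests three times, so both regression to the mean and practice are to be expected.

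At stake is a conclusion such as: patients with poorer baseline memory respond best to HD-tDCS. The data could show that with no treatment effect at all, and it could then steer selection for the next trial.

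**Working it through.** **Inputs from the documents.** 24 participants, 2:1 (Section 4): 24 × 2/3 = 16 active and 24 × 1/3 = 8 sham, so the split is consistent. No power calculation, significance level, SD or retest correlation is given, so there is no other planned figure to reproduce.

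**Assumed.** Correlation r between baseline and follow-up on the same test, 0.5 to 0.9; equal variances; normal scores; two-sided 5% test; one follow-up visit; no stimulation effect in anyone.

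**Built-in correlation.** Let B be baseline and F follow-up, each with variance 1.

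- cov(B, F-B) = r - 1
- var(F-B) = 2 - 2r
- corr(B, F-B) = -(1-r)/sqrt(2(1-r)) = -sqrt((1-r)/2)
- r = 0.6: -sqrt(0.20) = -0.45
- r = 0.7: -sqrt(0.15) = -0.39
- r = 0.8: -sqrt(0.10) = -0.32

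**How often this is significant with no effect.** In 20,000 simulated trials per value of r, testing the correlation of baseline with change:

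| r | 16 active only | all 24 |
|---|---|---|
| 0.6 | 43.8% | 61.6% |
| 0.7 | 32.3% | 47.8% |
| 0.8 | 22.7% | 33.0% |

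A second simulation (10,000 trials per value) regressed change on baseline, adjusting for group when all 24 were used. It also tested the group-by-baseline term:

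| r | 16 active only | all 24, main effect | all 24, group-by-baseline |
|---|---|---|---|
| 0.5 | 52.3% | 70.8% | 5.0% |
| 0.6 | 42.2% | 59.5% | 5.2% |
| 0.7 | 32.2% | 46.4% | 4.9% |
| 0.8 | 23.1% | 32.8% | 4.7% |
| 0.9 | 12.8% | 18.1% | 5.0% |

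The two agree closely. The interaction test holds its nominal 5% throughout. It was run on change, but with baseline in the model the interaction coefficient and its test are the same with the follow-up score as outcome, because subtracting B alters only the coefficient of B.

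**Predictors other than baseline scores.** There is no coupling here. A practice gain equal for everyone adds only a constant, so a problem arises only if the trait goes with the size of the shared gain. As an illustration, take a trait that raises the gain by 0.5 SD per SD in both arms, with residual SD sqrt(0.75) = 0.87 (both assumed). Its main effect on change is significant in about 71% of trials. That association is real, but it is prognostic and says nothing about response to stimulation.

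**Precision of the interaction with 16 and 8.** At r = 0.7 the residual SD is sqrt(1 - 0.49) = 0.71. Power for a between-arm slope difference of 0.3, 0.5, 0.8 or 1.0 SD per SD is 14%, 27%, 59% or 75%.

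**The case against.** The strongest reply is that Section 14 leaves the predictor model unspecified and does not specify a wrong one. The listed fixed effects contain no predictor at all, not even a main effect, so the list describes the efficacy model. Section 4 speaks of response compared with sham, so a sympathetic reader could take a predictor of response to mean a moderator of the active-sham difference. All of this stands. A reader might infer that the plan defines response solely as within-person change, or that it excludes the interaction. The documents support neither: the term is omitted, not ruled out.

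It is also fair that the error rates above belong to one plausible analysis at an assumed r. The protocol nowhere says that change will be regressed on baseline, or that the active arm will be examined alone. They should not be quoted as the error rate of this plan.

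Two further limits stand. Coupling applies only to a baseline score predicting change on the same or a correlated test. And the purpose stated in Sections 1 and 3 is efficacy; the predictor work is one additional sentence in a pilot, so finding responders should not be called a main aim.

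What the reply does not do is supply the missing term. The sympathetic reading needs a group-by-predictor interaction, and the only model and outcome scale on the page do not contain it.

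**Conclusion.** The point holds as a gap between the quantity named and the model stated. Section 14 promises predictors of response, Section 4 frames response relative to sham, and the stated change-score model cannot show whether any predictor alters the active-sham difference.

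If the predictor analysis is built from the stated pieces, as main effects or within the active arm, shared change can be reported as response. For baseline scores on the outcome test, that analysis would be significant in roughly 23-44% of null trials with 16 participants and 33-62% with 24, against a nominal 5%. These figures rest on r of 0.6 to 0.8, equal variances and a single follow-up. At r = 0.9 they fall to about 13% and 18%. For TBI severity, drug use and demographics the concern is shared practice or prognosis, and its size cannot be derived from the documents.

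A reader might infer that the main efficacy result is compromised. It is not: the randomised group*session contrast does not depend on how predictors are handled. This is a secondary analysis that should be corrected before the data are analysed.

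**What to change.** Replace the predictor sentence in Section 14 with wording such as: *Predictors of response will be tested as group-by-predictor interactions, by session (Visit 11 and Visit 12), with the follow-up score as outcome and the baseline score as covariate. Associations with outcome that are common to both arms will be reported as prognostic, not as response to stimulation. Because there are only 8 sham participants, these interactions are exploratory and will be reported as estimates with confidence intervals.* Where the predictor is the baseline score of the outcome test, that covariate serves as its main effect and only its interactions with group are added.

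The cost is SAP wording and a few model terms, with no new data, visits or participants. The downside is imprecision: with 16 and 8 participants only large differences in slope would be detected with reasonable probability, so the trial can claim less about who responds. A non-significant interaction should not be read as showing that response is uniform.
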